- 5. Previous kidney transplants will be permitted. Patients who are receiving a secondary transplant and who previously received Envarsus or who are currently on Envarsus as a component of maintenance immunosuppression and re-listed for transplant will be eligible to enroll in this study and will be randomized at the time of transplant to either cohort.
- 6. Subject agrees not to participate in another study while on treatment.
- 7. Female subject must be either:
 - a. Of non-child-bearing potential,
 - i. Post-menopausal (defined as at least 1 year without any menses) prior to screening, or
 - ii. Documented surgically sterile or status post-hysterectomy
 - b. Or, if of childbearing potential,
 - i. Agree not to try to become pregnant during the study and for 90 days after the final study drug administration
 - ii. And have a negative serum or urine pregnancy test within 14 days prior to transplant procedure
 - iii. And, if heterosexually active, agree to consistently use two forms of highly effective birth control (at least one of which must be a barrier method) which includes consistent and correct usage of established oral contraception, established intrauterine device or intrauterine system, or barrier methods of contraception: condom or occlusive cap (diaphragm or cervical/vault caps) with spermicidal foam/gel/film/cream/suppository, starting at screening and throughout the study period and for 90 days after the final study drug administration.
- 8. Male subject and their female spouse/partners who are of childbearing potential must be using highly effective contraception consisting of two forms of birth control (one of which must be a barrier method) starting at screening and continuing throughout the study period and for 90 days after the final study drug administration).
- 9. Female subjects must agree to not breastfeed from screening through end of the study period.

Waivers to the inclusion criteria will NOT be allowed. Patients meeting inclusion criteria at the time of randomization and not initiated on Envarsus or immediate-release tacrolimus within 48 hours of transplant will be classified as a recruitment failure and not included in the analysis.

Exclusion Criteria:

Subject will be excluded from participation if any of the following apply:

- 1. Patient is known to have a positive test for latent tuberculosis (TB) and has not previously received adequate anti-microbial therapy or would require TB prophylaxis after transplant.

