All patients will receive induction immunotherapy (either T-cell depleting agent or IL-2 co-stimulation blocker). The dose and frequency of the chosen induction agent will be determined by the patient's treating physician and administered in conjunction with the participating transplant center's *de novo* kidney immunosuppression protocol. As a participant in this study, in addition to tacrolimus, study subjects will need to concomitantly receive mycophenolate sodium (or MMF equivalent). Anti-CMV, fungal, bacterial, and pneumocystis prophylaxis will follow standard of care. Non-tacrolimus based immunosuppressive regimens (i.e. cyclosporine, everolimus, sirolimus, belatacept), as well as all forms of extended-release tacrolimus other than Envarsus, are prohibited during the course of the study. *Measures to Treat Rejections:* The need for therapy to treat rejection will be determined by the supervising physician. Typical rescue drugs employed under these conditions include, but are not limited to rabbit anti-thymocyte globulin, intravenous immunoglobulin (IVIG), rituximab, and eculizumab.

Duration of Treatment:

Study enrollees will receive study medication (single daily dose of Envarsus or standard of care twice daily, immediaterelease tacrolimus) for up to one year following their transplant procedure.

Formal Stopping Rules:

A decision to terminate the study early will be based on the event rate of rejections or AE's as determined by the Research Committee of the Renal Transplantation Service comprised of all nephrologists, surgeons, and transplant coordinators which meets monthly. The study duration will be such that patients will complete at least one year of study visits. Interim data analysis will be performed once all patients complete 6 months of study and final analysis will be performed when all patients complete 12 months of study.

Discontinuation Criteria from Treatment for Individual Subjects:

Subject develops allograft loss (as defined by subject death, re-transplantation, transplant nephrectomy, or return to dialysis of \geq 6 consecutive weeks);

Subject develops unacceptable toxicity or is withdrawn at the discretion of the patient's supervising physician; Subject is lost to follow-up despite reasonable efforts by the investigator to locate the subject;

Subject withdraws consent for further treatment;

Conversion to a non-tacrolimus-based maintenance regimen in either study arm if required to manage toxicities.

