
Version Date: 11Jun2019 10 of 16

Study Visits

Screening Period

The screening period can be any time from 21 days before your transplant until the day of transplant. At the screening visit, the following procedures and tests will be performed:

-A review of current health status, medical and surgical history, and list of medications

-Collection of blood samples for clinical purposes.

-A physical examination (including height and weight)

- Questions about any side effects that may occur from the medications taken.

-Female participants who are able to have children will also have a pregnancy test (either from a blood draw or a urine sample) within the 14 days before the kidney transplant as per standard-of-care.

For deceased donor, the screening and randomization procedures may take place on the day of transplant.

For living donors, randomization procedures may take place on the day of transplant.

Randomization

Subjects will be randomized to two open label treatment arms in a 1:1 ratio by a computer program. The two treatment arms are: Treatment Arm 1: Study medication is once daily Envarsus, or slow-release tacrolimus; Treatment Arm 2: Study medication is twice daily, Prograf, or immediate-release tacrolimus. Randomization will happen the day of transplant to ensure all questions have been answered prior to surgery and the subject wishes to remain in the study.

Subjects randomized to Envarsus will need to take the study medication once a day at the same time each day, by mouth. For both treatment arms, the medications that you take in preparation for your kidney transplant ("induction therapy") and the other medications that the study medication needs to be taken with (including steroids and mycophenolate mofetil [MMF]) will be given to you in the way your doctor normally gives them. These medicines will not be paid for or reimbursed by the study sponsor because they need to be taken whether or not you are in the study. ONLY the study medication Envarsus will be provided to you by the sponsor for no charge.

Follow Ups

Both Arms of the study will have the same 11 planned study visits to the research center, which will be done monthly post-transplant until the 1 year follow up is completed. When possible, all visits will be done in conjunction with standard-of-care-follow up visits with the nephrologist. If the subject is unable to return for an in-person appointment, a phone call visit will be used in its place with the research staff.

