Medical History: Etiology of renal failure, viral serology (HBV, HCV, CMV, EBV), and diabetes history (as applicable). *Transplant Information*: Day 0 visit: type of transplant (living related, living non-related, DD, and whether organ was obtained in the setting of DCD or CDC), number of prior transplants and reason for prior graft loss (if applicable), total cold and warm ischemia time in hours and minutes, KDPI, ABO blood typing, HLA typing of donor and recipient, degree of HLA mismatch between donor and recipient, and most recent panel reactive antibody testing. Donor viral serology information (HBV, HCV, CMV, EBV), if available, will be collected and recorded. Additional donor information includes age, sex, height, weight, donor cause of death, ethnicity, ABO typing, and results of any pre-implantation biopsies. *Height and Body Weight*: Height and dry weight will be recorded at screening and pre-operatively on study day 0.

Efficacy Assessment

Estimated Glomerular Filtration Rate: Estimated glomerular filtration rate (eGFR) will be calculated at day 7 and months 1, 3, 6, and 12 using the Modification of Diet in Renal Disease (4 variable – MDRD) criteria.

Calculation of C/D Ratio: Calculation of the daily trough level over the average daily total tacrolimus dose delivered either by ENVARSUS or by SOC twice a day Tacrolimus will be performed monthly throughout the study.

Patient Survival: Patient survival is any subject that is known to be alive at the study conclusion.

Graft Survival: Graft survival is defined as any subject that does not fit the following definition of graft loss: subject death, re-transplantation, transplant nephrectomy, or return to dialysis for a period of ≥6 weeks by study end. *Acute Rejection*: For study purposes, diagnoses of rejection require biopsy confirmation. Both acute cellular and antibody mediated rejection will be assessed and graded according to published criteria [Solez et al, 2008] by the NYPH

Renal Pathology Division pathologist.

Adverse Events

Adverse event collection will begin once informed consent has been signed and continue throughout the subject's participation in the study. A subset of the routine laboratory assessments obtained per SOC, including creatinine, hemoglobin, hematocrit; platelet count; white blood cell count; serum sodium, potassium, blood urea nitrogen, glucose, urinalysis (including urinary protein), tacrolimus trough concentrations.

Physical Examination

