All AEs occurring during the study are to be followed up until resolved or judged to be no longer clinically significant, or until they become chronic to the extent that they can be fully characterized. If during AE follow-up, the adverse event progresses to an "SAE", or if a subject experiences a new SAE, the investigator must immediately report the information to the Sponsor. Local IRB will inform the investigator that some events reported as SAEs may not require expedited reporting to the IRB. The Sponsor will monitor these events throughout the course of the study.

Version Date: 11Jun2019 13 of 16

Procedure in Case of Pregnancy

If a female subject or partner of a male subject becomes pregnant during the study dosing period or within 30 days from the discontinuation of dosing, the investigator should report the information as an SAE. The expected date of delivery or expected date of the end of the pregnancy, last menstruation, estimated conception date, pregnancy result and neonatal data etc., should be included in this information. The medical status of the mother, as well as the fetus, will be followed and outcome reported to the IRB.

DISCONTINUATION

Discontinuation is defined as a subject who enrolled in the study and for whom study treatment is permanently discontinued prematurely for any reason. The subject is free to withdraw from the study treatment and/or study for any reason and at any time without giving reason for doing so and without penalty or prejudice. The investigator is also free to terminate a subject's involvement in the study at any time if the subject's clinical condition warrants.

Discontinuation Criteria from Treatment for Individual Subjects:

- Subject develops allograft loss (death, re-transplantation, transplant nephrectomy, or return to dialysis ≥ 6 consecutive weeks);
- Subject develops unacceptable toxicity or is withdrawn at the discretion of the patient's supervising physician;
- Subject is lost to follow-up despite reasonable efforts by the investigator to locate the subject;
- Subject withdraws consent for further treatment or expires during the course of the study;
- Conversion to a non-tacrolimus-based maintenance regimen in either study arm if required to manage toxicities;

OPERATIONAL AND ADMINISTRATIVE CONSIDERATIONS

Data Collection

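### Pregnancy reporting stops at conceptions 30 days after the last dose, while contraception is required for 90 days, so conceptions on days 31 to 90 need not be reported or followed.

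*Combined protocol and SAP*

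**What the plan says.** The Inclusion Criteria set the same post-dose period three times.

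- Item 7.b.i, women of childbearing potential: "Agree not to try to become pregnant during the study and for 90 days after the final study drug administration".
- Item 7.b.iii, two forms of birth control for heterosexually active women of childbearing potential: "starting at screening and throughout the study period and for 90 days after the final study drug administration".
- Item 8, male subjects and partners of childbearing potential: "starting at screening and continuing throughout the study period and for 90 days after the final study drug administration".

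Procedure in Case of Pregnancy sets the reporting duty. It asks for an SAE report when a woman in the trial, or a male participant's partner, conceives while dosing continues or "within 30 days from the discontinuation of dosing". That section is the only place that calls for following mother and fetus and sending the outcome to the IRB.

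The Adverse Events section sets the general collection period: "Adverse event collection will begin once informed consent has been signed and continue throughout the subject's participation in the study". Under Follow Ups and the Schedule of Events, visits are monthly and end at month 12, with a tolerance of 2 weeks. The schedule also marks a pregnancy test for women of childbearing potential in the Month 1 to Month 12 column.

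**The concern.** By asking for two forms of birth control for 90 days, the protocol treats that period as one in which pregnancy should be prevented. It should then also say what happens if prevention fails. The reporting rule covers the same people and counts from the same event, the end of dosing, but ends 60 days sooner. The documents give no reason for the difference.

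What is at stake is safety information. For a conception on days 31 to 90, the protocol gives the investigator no stated duty to report the pregnancy, follow mother and fetus, or send the outcome to the IRB.

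**Working it through.** The plan states no figure on this point, so there is none to reproduce.

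**Inputs**

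- Post-dose contraception: 90 days (Inclusion Criteria 7.b.i, 7.b.iii and 8).
- Post-dose pregnancy reporting: 30 days (Procedure in Case of Pregnancy).
- Dosing: "for up to one year following their transplant procedure" (Duration of Treatment), taken as 365 days.
- Screening: "The screening period can be any time from 21 days before your transplant until the day of transplant" (Screening Period), so at most 21 days.

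**Step 1. Uncovered part of the post-dose period**

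- Days: 90 − 30 = 60, namely days 31 to 90.
- Share: 60/90 = 66.7%, or two thirds.

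**Step 2. The same 60 days over the whole contraception period**

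| Case | Calculation | Share |
|---|---|---|
| Dosed 365 days, no screening time counted | 60/(365 + 90) = 60/455 | 13.2% |
| Dosed 365 days, longest screening | 60/(21 + 365 + 90) = 60/476 | 12.6% |
| Dosed 180 days (assumed), then leaves the study | 60/(180 + 90) = 60/270 | 22.2% |
| Dosed 30 days (assumed), then leaves the study | 60/(30 + 90) = 60/120 | 50.0% |

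These shares count only the gap after the last dose. The last two rows are illustrations; the documents give no expected time to early discontinuation.

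**Step 3. Does another section cover days 31 to 90?**

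- *Visits.* For a subject dosed to one year, the last visit can fall at most 14 days after month 12. That is before day 31, so no scheduled contact falls in the gap.
- *General AE collection.* It ends with participation, and Follow-up of Adverse Events concerns events that occur during the study. No section says that a pregnancy by itself counts as an adverse event.
- *Scheduled pregnancy tests.* They stop at month 12 and do not apply to partners.
- *Protocol Deviations.* The notifiable deviations are unmet entry criteria, wrong treatment or dose, and excluded concomitant treatment. A lapse in contraception or a pregnancy is not among them.

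**Step 4. Subjects who stop drug early but stay in the study**

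The reporting rule ends 30 days after dosing stops, while the contraception commitment also runs throughout the study. For these subjects the days outside the reporting rule can exceed 60. They do remain under visits, AE review and, for women of childbearing potential, pregnancy testing. A test could thus find a pregnancy that the pregnancy section does not require anyone to report.

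**The case against.** **The rules do not conflict.** One is a commitment made at entry and the other is an investigator's reporting duty. Both can be followed in full, and nothing in the documents says that the windows must be equal. This stands: a reader might infer a contradiction, but the text supports only an unexplained mismatch.

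**Two thirds can mislead.** A reader might take it as the share of all the time in which pregnancy is to be prevented. The documents do not support that, because conceptions during dosing are reportable. Over the whole contraception period the share is about 13% for a subject dosed for a year.

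**The text does not forbid reporting.** A reader might infer that these pregnancies will go unreported. The section only limits when a report is required, and an investigator may report later ones. The window also depends on when pregnancy begins, so a conception by day 30 that is discovered later is still reportable.

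**Some subjects have partial cover.** A woman who stops early but stays in follow-up may pass through days 31 to 90 under visits and testing. This stands for her, but it does not reach partners or time after month 12.

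**The numbers are small.** The trial enrols 50 recipients aged 18 to 80 and requires contraception. The measure above counts calendar days, not pregnancies. This also stands and limits the weight of the point, but it does not explain the shorter window.

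**Conclusion.** The concern holds in limited form. Conceptions on days 31 to 90 after the last dose fall inside the contraception period and outside the duty to report and follow. The size is 60 of 90 post-dose days, and 12.6% to 13.2% of the whole contraception period for a subject dosed for a full year.

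This rests on three readings:

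- both windows are counted from the last dose;
- the reporting window is set by when pregnancy begins;
- pregnancy alone is not an adverse event outside its own section, since no section says that it is.

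The documents do not give the number of women of childbearing potential or of male subjects with such partners, so no expected number of pregnancies can be calculated. It is likely to be small. The efficacy comparison is unaffected. The point is worth acting on because it concerns safety follow-up and is cheap to correct.

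**What to change.** Reconcile Inclusion Criteria 7 and 8 with Procedure in Case of Pregnancy, so that pregnancy reporting and follow-up cover the post-dose contraception period that the protocol itself sets, for subjects and for partners. Uncovered post-dose time would then fall from 60 of 90 days to 0 of 90. This review takes no position on how long contraception should last.

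The wording should also hold for a subject who stops drug early but stays in the study. Because no visit is scheduled after month 12, the amendment should say how the site will learn of a later pregnancy. In practice that means asking subjects to notify it.

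The cost is a short amendment, which under Protocol Amendment and/or Revision needs approval by the sponsor, the investigator and the IRB. A consent update may be needed, and a few extra reports at most should follow. Capture after month 12 would depend on subjects coming forward, so it would be improved but not assured.

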This is a one year, prospective, randomized, open-label trial examining once versus twice daily tacrolimus dosing regimen using two preparations, Envarsus vs Prograf. It will examine kidney function between the two groups using eGFR and also examine one year kidney outcomes, including graft loss and patient death. Biopsy will be performed on clinical indications only (not protocol) when rejection or other problem is suspected in face of deteriorating renal function in each study group utilizing Banff criteria. Patients will be screened prior to surgery and randomized 1:1 to receive, within 48 hours of transplantation, immediate release tacrolimus, administered twice daily, or Envarsus, administered once daily as a component of a standard immunosuppression maintenance regimen also consisting of mycophenolate sodium (MPA) (or mycophenolate mofetil equivalent). Induction therapy will be given and administered per center protocol (rabbit anti-thymocyte globulin 6mg/kg over 4 days except in HLA identical living donor/recipient pairs when basiliximab induction is used intraoperatively). Intravenous corticosteroids (methylprednisolone 500mg intraoperatively with a daily rapid taper to 250, 125, 80 mg) over 4 days will be administered prior to rabbit antithymocyte globulin and prior to revascularization as part of the initial induction regimen. Thereafter, patients will be followed for up to 1 year during the open label study period. After discharge from the hospital, the patients randomized to immediate-release tacrolimus will be permitted to receive any immediate release tacrolimus product available to them through normal dispensing mechanisms. Envarsus will be supplied by Veloxis and dispensed by the research pharmacy.

Inclusion Criteria:

Subject is eligible for the study if all of the following apply:

1. Kidney transplant patient \ge 18 years and \le 80 years old

- 2. Institutional Review Board (IRB) approved written Informed Consent and privacy language must be obtained from the subject prior to any study-related procedures (including withdrawal of prohibited medication, if applicable).
- 3. Recipient of a *de novo* kidney from a living or deceased donor.
 - a. If deceased donor, a Kidney Donor Profile Index (KDPI) ≤ 85% are eligible for enrollment.
- 4. Willingness to comply with study protocol.

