Clinical Laboratory assessment	Х			Х
Pregnancy test (WOCBP only)	X			X
Concomitant Medications	Х	Х	Х	Х
Adverse Events	Х	Х	Х	Х
Study drug accountability			Х	X

¹Height and Body Weight: Height and dry weight will be recorded at screening and pre-operatively on study day 0. ²For living donors, the randomization will happen at the pre-operation check-up at the hospital, which happens about 7 days before transplant operation. For deceased donors, the randomization will happen at admission for the transplant operation. ³Month 1 to Month 12 Visits will be conducted in conjunction with SOC visits. Adverse events and drug accountability will be reviewed for research purposes.

Version Date: 11Jun2019 16 of 16

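### Two sections give living-donor recipients different randomisation times, and the earlier one lengthens the gap in which randomised patients can drop out of the analysis

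*Combined protocol and SAP*

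**What the plan says.** The protocol sets the time of randomisation in several places.

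- Schedule of Events, footnote 2, living donors: "the randomization will happen at the pre-operation check-up at the hospital, which happens about 7 days before transplant operation".
- The same footnote, deceased donors: "For deceased donors, the randomization will happen at admission for the transplant operation".
- Study Visits, Randomization, all subjects: "Randomization will happen the day of transplant to ensure all questions have been answered prior to surgery". The sentence goes on to give a second purpose, that the subject still wants to be in the trial.
- Study Visits, Screening Period: "For living donors, randomization procedures may take place on the day of transplant".
- Inclusion Criteria, item 5: repeat-transplant patients with previous or current Envarsus "will be randomized at the time of transplant to either cohort".

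Three further statements decide what the timing means for the analysis.

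- Masking (Randomization section): "Subjects will be randomized to two open label treatment arms in a 1:1 ratio by a computer program".
- Start of treatment (Study Design Overview): "Patients will be screened prior to surgery and randomized 1:1 to receive, within 48 hours of transplantation, immediate release tacrolimus", or Envarsus. The Schedule of Events first marks dispensing of study drug in the Day 0 column.
- Non-starters (end of Inclusion Criteria): patients who met the criteria when randomised but were not started within 48 hours of transplant "will be classified as a recruitment failure and not included in the analysis".

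**The concern.** The footnote and the Randomization section are both mandatory, and both are current text. A coordinator who randomises a living-donor recipient at the check-up breaches one; a coordinator who waits until the day of surgery breaches the other. The footnote also defeats the purpose that the Randomization section gives for its rule, since a wish to continue that is confirmed a week before surgery may have changed by the day.

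The statistical stake comes from the rule on non-starters. The longer the interval between allocation and first dose, the more chance there is that a randomised patient withdraws, or that surgery is put off and treatment never starts within the trial. Each such patient leaves the analysis after randomisation. The arms are open label and no section says that the assignment is held back until surgery, so withdrawal could depend on the arm. Under the footnote the long interval applies to living-donor recipients only. The Statistical Analysis section hopes to read trends separately in living-donor and deceased-donor recipients, so selective loss would fall in a group that the pilot means to interpret.

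**Working it through.** **The plan's own figure.** The planned size is 25 + 25 = 50. The protocol gives no effect size, SD, power or dropout rate, so nothing more can be reproduced. The main check is a comparison of sections.

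**Is there a contradiction?** For living-donor recipients the footnote fixes about day -7 and the Randomization section fixes day 0. Both use *will*, and neither makes an exception for the other. The Screening Period sentence uses *may*; it permits day 0 and can stand beside the footnote. Item 5 of the Inclusion Criteria places a subgroup at the time of transplant, in line with the Randomization section. The conflict is therefore between the footnote's living-donor clause and the Randomization section.

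**Gap from allocation to first dose.** Gap = day of first dose minus day of randomisation, reading the 48-hour limit as counted from surgery (first dose on day 0 to 2).

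- Footnote 2: 0 - (-7) = 7 days, up to 2 - (-7) = 9 days.
- Randomization section: 0 - 0 = 0 days, up to 2 - 0 = 2 days.

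**How many patients might be lost.** The documents give neither the share of living-donor recipients nor a pre-transplant loss rate. I assume 30-70% and 2-10%. Expected losses = 50 × share × rate; P(at least one) = 1 - (1 - rate)^n, where n = 50 × share.

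| Share (n) | Rate | Expected losses | P(at least one) |
|---|---|---|---|
| 30% (15) | 2% | 15 × 0.02 = 0.3 | 1 - 0.98^15 = 0.26 |
| 50% (25) | 5% | 25 × 0.05 = 1.25 | 1 - 0.95^25 = 0.72 |
| 70% (35) | 10% | 35 × 0.10 = 3.5 | 1 - 0.90^35 = 0.975 |

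**Effect on precision.** With an assumed two-sided 5% level and 80% power, detectable difference = (1.960 + 0.842) × √(2/n per arm) in SD units.

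- 25 per arm: 2.802 × √(2/25) = 0.79 SD.
- 23 per arm (4 patients lost, just above the top of the range): 2.802 × √(2/23) = 0.83 SD.

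**Effect of selective loss.** If 2 of 25 patients in one arm are lost and differ by 1 SD (assumed) from those retained, that arm's mean shifts by 2/25 × 1 = 0.08 SD.

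**The case against.** The strongest reply is that the two times do conflict, but that little follows from it. Several parts of that reply stand.

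- A reader might infer that patients and staff know the arm for a week. The documents do not say this. Open label means that treatment is not masked; it does not say when the assignment is disclosed. One could even read the footnote as drawing the assignment at the check-up and revealing it later, although no section says so. Knowledge of the arm during the gap is therefore possible, not established.
- A reader might call it an untreated week. No study drug is due in either arm before transplant, so no treatment is missed.
- A reader might take the Screening Period sentence as a further contradiction. It is permissive and does not conflict.
- A reader might say that nothing is checked between allocation and surgery. The Schedule of Events marks concomitant medications and adverse events in both the Randomization and Day 0 columns, and Protocol Deviations makes entry of an ineligible patient notifiable. Laboratory tests and the pregnancy test are not marked in those columns. However, a pregnancy test done at the check-up stays inside its 14-day window unless surgery is postponed.
- The loss rates are assumptions, and at the low end fewer than one patient is expected. A postponed patient who is later transplanted and started on time is not excluded at all. The protocol also describes itself as an underpowered pilot.

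These points limit the size of the concern. They do not reconcile the two instructions, and they leave the rule on non-starters in place.

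**Conclusion.** The concern holds in a limited form. The protocol gives two incompatible randomisation times for living-donor recipients. The footnote lengthens the interval from allocation to first dose from about 0-2 days to about 7-9 days, and the rule on non-starters turns losses in that interval into post-randomisation exclusions.

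The size is unknown from the documents. Under the assumed ranges it is 0.3 to 3.5 of 50 patients, with a small cost in precision. The issue is possible selective exclusion and an instruction that cannot be carried out as written, not power.

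It would go too far to conclude that randomising on the day of transplant settles the matter without any change to reporting. The rule on non-starters covers both donor types and still applies during surgery and the 48 hours after it, so randomised patients could still be dropped. The shorter gap reduces the opportunity for loss but does not remove it.

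**What to change.** Amend footnote 2 so that both donor types are randomised at admission on the day of transplant, after consent and eligibility are reconfirmed and before surgery. Align the *may* sentence under Screening Period with it. The pre-operative check-up can then serve for consent and screening, which fits the rule under Patient Recruitment that living-donor recipients are not first approached on the day of transplant.

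In the Statistical Analysis section, add that patients randomised but not started will be reported by arm and donor type, with the reason.

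The cost is a minor amendment, which under Protocol Amendment and/or Revision needs the approval of the sponsor, the investigator and the IRB. In practice, the arm assignment and the notice to the research pharmacy for living-donor recipients would come on the day of surgery, as the footnote's admission rule already requires for deceased-donor recipients. The sample size and the trial procedures stay as they are.
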